The overall aim of EU-SolidAct is to evaluate the safety and efficacy of therapeutic agents in hospitalized patients diagnosed with SARS-CoV-2, to reduce overall mortality and morbidity, as well as burden of disease on the health systems.

General master study details include:

EU-SolidAct Master Protocol version 2.2

- The study duration will be up to 90 days (± 14 days) for each participant.
- The treatment duration will be defined in the investigational-specific subprotocols.
- The assessment frequency:
 - Participants will be screened, assessed for eligibility and enrolled as soon as possible after admission.
 - Baseline assessments and randomization at Day 1 as soon as possible after screening.
 - Day 3, 5, 8 (± 1 day) assessments during hospitalisation, then weekly visits until discharge (Day 15 ± 3 , Day 22 ± 3 , Day 29 ± 3 , etc.).
 - Assessments at Day 15 ± 3 , Day 29 ± 3 , Day 61 ± 7 (end points) and Day 91 ± 14 (end of study) will be done at hospital (if participants are still hospitalized); or in the outpatient setting or by phone (if participants are discharged from hospital).
- Number of enrolled Participants:
 - For phase 3 *superiority trials* approximately 1000 participants will be screened to achieve 950 randomly assigned to each arm in Part A and approximately 1000 participants will be screened to achieve 950 randomly assigned to each arm in Part B. For phase 3 *non-inferiority trials*, about 3000 in each arm is needed. For phase 2 trials, about 200 in each arm will be included.
 - Where combination therapies are assessed by factorial design, the main assumption will be that no interaction exists between the treatments and therefore no modification of the sample size will be planned. If synergies or effect modifications between treatments are of interest, the intervention-specific sub-protocols will define the sample size needed for detecting the interaction effect.

Note: *Enrolled* means a participant, or his/her legally authorised representative, has provided informed consent to participate and has been screened and found eligible for the trial. The participant will *not* be considered enrolled if the informed consent has been withdrawn prior to participating in any other study activity than screening.

- Intervention Groups and Duration:
 - Detailed in the intervention-specific sub protocols.
- Data Monitoring:

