3.1. Phase 3 Trial Objectives and Endpoints

In phase 3 confirmatory trials, the primary objectives and endpoints are described below. Secondary objectives and endpoints as listed below should be considered for all interventions studied within this platform. The final selection and any additional intervention-specific objectives or endpoints will be described in corresponding sub-protocols.

Table 3.1 Phase 3 objectives and corresponding endpoints

Objectives	Endpoints
Primary	
Part A, moderate disease	
The primary objective is to determine the effect of therapeutic interventions on occurrence of disease progression in hospitalized patients with moderate COVID-19	Occurrence of disease progression, defined as a progression of disease state from moderate (WHO score 4-5) to severe/critical (WHO score 6-9) or death (WHO score 10) within 14 days
Part B, severe disease	
The primary objective is to determine the effect of therapeutic interventions on occurrence of death in hospitalized patients with severe or critical COVID-19	Occurrence of death within 60 days
Secondary	
Secondary objectives are 1. to determine the effect of therapeutic interventions on other clinical endpoints	1.1 Occurrence of disease progression, defined as a progression of disease state from moderate (WHO score 4-5) to severe/critical/death (WHO score 6-10) or from severe/critical (WHO score 6-9) to death within 28 days 1.2 Time from randomization to sustained recovery, defined as being discharged from the index hospitalization, followed by being alive and at home for 14 consecutive days within 90 days

	
1.3 Time from randomization to first hospital discharge within 90 days
 
1.4 Disease state on a 5-point scale defined as:
 
 1. Mild (WHO score 1-3) or better, 2. Moderate (WHO score 4-5), 3. Severe (WHO score 6), 4. Critical (WHO score 7-9) or 5. Death at Day 15 and 29 
1.5 Time from randomization to recovery defined as no need for oxygen
 
1.6 SpO₂/FiO₂-ratio at day 3, 5 and 8

2. to determine the effect of therapeutic interventions on viral clearance	2. Viral clearance as assessed by SARS-CoV-2 PCR in oropharyngeal specimens during hospitalization

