 - If ferritin and procalcitonin are not routinely gathered at a site for clinical follow-up of the patient, these analyses should be prioritized at baseline, D8 and D15.
- Obtain vital signs including height in cm and weight in kg, see section 8.3.2.
- Collect data on oxygen therapy, see section 8.1.2.
- Register WHO COVID-19 disease progression scale (0-10), see section 8.1.1.
- Details of study treatment administration according to intervention-specific sub-protocol

Assessment until discharge:

Participants will be assessed daily for AE and SAE while hospitalized, see section 8.6.

- Note AE and SAE in the eCRF upon notice
- Safety concerns should be discussed with the sponsor to determine if the participant should continue or discontinue study intervention

The following clinical data will be noted in the eCRF obtained on Days 3, 5, 8 (± 1 day), and thereafter weekly (Day 15 ± 3 , Day 22 ± 3 , Day 29 ± 3 , etc.)

- Obtain vital signs, see section 8.3.2.
- Collect data on oxygen therapy, see section 8.1.2.
- Register WHO COVID-19 disease progression scale (0-10), see section 8.1.1.
- Review concomitant medication and note changes in the eCRF
- Draw and register blood samples for clinical safety laboratory tests (see section 8.3.5.)
 - If ferritin and procalcitonin are not routinely gathered at a site for clinical follow-up of the patient, these analyses should be prioritized at baseline, D8 and D15.

Details of study treatment adherence and administration will be given in the intervention-specific sub-protocol.

For level II of commitment:

Blood samples and naso/oropharyngeal swabs should be obtained at baseline (D1) before drug intervention starts. In addition, blood samples will be obtained on Days 3, 8, 15 and 22 (all ± 1 day), and naso/oropharyngeal swabs on Days 3, 8, 15 (all ± 1 day), as long as the patient is hospitalized.

Day 15 ± 3 , 29 ± 3 , 61 ± 7 :

If the patient has been discharged, the following information is gathered by phone or by reviewing the patient records:

- Alive or dead

If alive, recovery status

- Readmitted to hospital
- If readmitted, date of readmission and reason for readmission. Report as SAE.
- Review concomitant medication
- Adverse events by open-ended and non-leading verbal questioning of the participant

Follow-up assessment at Day 91 ± 14 :

A follow-up assessment by phone will be performed on Day 91 (± 14 days):

- Alive or dead

If alive, recovery status

- Readmitted to hospital

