9.3.3. Secondary endpoint(s) analysis

The occurrence of disease progression, defined as a progression of disease state from moderate (WHO score 4-5) to severe/death (WHO score 6-10) or from severe (WHO score 6-9) to death within 28 days will be estimated using Kaplan-Meier estimates. The same methodology will be used for these endpoints than the one described in section 9.3.2.

The median time from randomization to sustained recovery, with sustained recovery defined as being discharged from the index hospitalization, followed by being alive and home for 14 consecutive days within 90 days will be estimated using the Kaplan-Meier method. The log-rank test will be used to compare each study intervention and the control survival functions. Participants will be censored at the date of lost to follow-up or at the 90th day after randomization when the participant has not achieved the event before. The effect of study intervention on the time to sustained recovery will also be assessed using Cox regression model with treatment group and adjustments for stratification factors.

The median time from randomization to first hospital discharge within 90 days will be analysed with the methodology described above.

Continuous endpoints will be analysed using analyses of covariance adjusted by stratification factors in the randomization and baseline value if applicable, or appropriate (generalised) linear mixed model with random intercept and possibly slope for repeated measures.

For the analysis of disease state on a 5-point scale a proportional odds model will be used. The hypothesis test will be based on a test of whether the common odds ratio for treatment is equal to one. Model fit will be evaluated using a goodness-of-fit likelihood ratio test. The distribution of severity results will be summarized by treatment arm as percentages. The validity of the proportionality assumption will be evaluated and tested.

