Similarly, assuming a 15% mortality for the SoC group in Part B and a 2-sided type-1 error rate of 5% and using the Log-Rank test, the study will have over 90% power with a sample size of 924, 521 and 378 per arm to detect a treatment difference of 5%, 6.5% and 7.5% respectively. We hypothesize that a treatment difference in mortality rates at day 61 of 5% seems achievable. Therefore, we plan to enrol 950 participants per arm, considering potential drop-outs before the assessment of the primary endpoint at day 61

Table 9.3: Sample size calculation in EU-SolidAct Part B superiority trial

	Scenario 1	Scenario 2	Scenario 3
Outcome (Death at day 61)			
Hypothesized event rate with SoC	15%	15%	15%
Expected event rate with intervention	10%	8.5%	7.5%
Type I error (two-sided)	0.05	0.05	0.05
Power	90%	90%	90%
Hazard ratio (HR)	0.648	0.547	0.48
N per group	924	521	378
Total number of events required	224	115	78

In case combination therapies are assessed by factorial design, the main assumption will be that no interaction exists between the treatments and therefore no modification of the sample size will be necessary. If synergies or effect modifications between treatments are of interest, the intervention-specific sub-protocols will define the sample size needed for detecting the interaction effect.

For a non-inferiority trial, assuming a 15% primary endpoint rate (progression in Part A and mortality in part B) in the active comparator arm, a non-inferiority margin of 3%, a 95%

confidence interval of the effect size and a 90% power, we need to enrol 3000 participants per arm

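### Section 9.3.3 censors participants without sustained recovery at day 90 although the last contact may validly fall on Day 77, so up to 14 unobserved days are analysed as observed non-recovery (minor)

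*Protocol*

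**What the plan says.** - **Last contact.** Section 8, under the Day 91 follow-up: "A follow-up assessment by phone will be performed on Day 91", with a window of ±14 days. The schedule of assessments (Section 1.2) gives the same window and labels the visit end of study. The synopsis says: "The study duration will be up to 90 days", again ±14 days. Under Section 4.4 this is the last scheduled procedure, and it completes participation.
- **Endpoints.** In Table 3.1, endpoint 1.2 requires discharge "followed by being alive and at home for 14 consecutive days within 90 days". Endpoint 1.3 is: "Time from randomization to first hospital discharge within 90 days".
- **Censoring for 1.2 and 1.3.** Under Section 9.3.3, those without the event are "censored at the date of lost to follow-up or at the 90th day after randomization". The section then applies the same methodology to first discharge.
- **Loss to follow-up.** Section 7.3 defines it as being unreachable after discharge.
- **Censoring for the primary endpoints.** Section 9.3.2 uses a different rule: participants without final outcome data are censored at the date of last information, with worst-case and best-case sensitivity analyses.
- **Source of data after discharge.** Footnote 8 of the schedule allows telephone contact, patient records, the primary caretaker or relatives. It sets no date before which this may not be done.

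**The concern.** The 90-day horizon, the window of the last contact and the censoring date do not fit together. Where the last contact comes before Day 91, the days between it and day 90 are unseen. Section 9.3.3 offers only two censoring dates. The first, loss to follow-up, does not apply to someone who answered the phone, so the second, day 90, does. Unseen time is then entered as time at risk without recovery.

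Sustained recovery is the exposed endpoint because it takes 14 further days at home to complete. Take a participant who goes home on Day 66, is called on Day 77 and stays well. That participant recovers on Day 80 but is analysed as not recovered through day 90. At stake are the last part of the recovery curve, the estimated proportion recovered by day 90 and, to a lesser degree, the log-rank and Cox comparisons. The amount of truncation depends on when each site happens to call.

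**Working it through.** The protocol states no figure for this point, so there is nothing to reproduce. The check is calendar arithmetic followed by an illustration.

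**Day convention.** Randomization is Day 1, so study Day k is k − 1 days after randomization. This agrees with the protocol's pairs Day 15/14 days, Day 61/60 days and Day 91/90 days.

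**Step 1: the uncovered tail.** Day 91 ± 14 is Day 77 to Day 105, or 76 to 104 days after randomization. The horizon is 90 days. The largest gap is 90 − 76 = 14 days, and 14/90 = 15.6%.

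**Step 2: who loses an event (1.2).** A participant home from day d after randomization completes the endpoint at d + 14. A call 76 days after randomization can confirm only d + 14 ≤ 76, that is d ≤ 62 (study Day 63). True events need d + 14 ≤ 90, that is d ≤ 76. The affected group went home 63 to 76 days after randomization, including those whose 14-day count restarted after a readmission. All of them are already home when called.

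**Step 3: who could be affected for first discharge (1.3).** Only participants still in hospital at an early final visit. Inpatients have weekly visits until discharge and a separate discharge visit, so the discharge is missed only if the early final visit closes follow-up. The text permits that but does not settle it.

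**Step 4: the other endpoint windows.**

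| Contact | Earliest day | Days short of horizon | Earliest day of next contact |
|---|---|---|---|
| Day 15 ± 3 | 12 | 3 | 26 (Day 29 − 3) |
| Day 29 ± 3 | 26 | 3 | 54 (Day 61 − 7) |
| Day 61 ± 7 | 54 | 7 | 77 (Day 91 − 14) |
| Day 91 ± 14 | 77 | 14 | none |

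For the first three, the next contact always falls beyond the horizon. Only Day 91 has nothing behind it.

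**Step 5: illustration of size.** These assumptions are not in the protocol: exponential time to discharge home with median m of 15 to 40 days, and a share S of 70 to 90% with sustained recovery by day 90. Let λ = ln 2/m, F(t) = 1 − exp(−λ(t − 14)) and c = S/F(90).

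- All last calls on Day 77: lost share = c[F(90) − F(76)]. For S = 0.8 and m = 25, λ = 0.0277, F(90) = 0.878, F(76) = 0.821, c = 0.911, and the lost share is 5.25%, about 50 of 950. Over the whole grid it is 2.0 to 9.0%, about 19 to 86 of 950 per arm.
- Calls spread evenly over the 29 days of the window: average c[F(90) − F(v)] over v = 76 to 104, counting zero from v = 90 on. For the same example this is 1.28%, about 12 of 950. Over the grid it is 0.5 to 2.3%, about 4 to 21 of 950. Under even spread 14/29 = 48% of calls come before Day 91, but that counts early calls, not misclassified participants.

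**Step 6: the median.** The rule alters nothing before 76 days after randomization. In the slowest scenario (S = 0.7, m = 40), λ = 0.0173, F(90) = 0.732 and c = 0.956. The curve reaches 50% where F = 0.5/0.956 = 0.523, at t = 14 + 0.740/0.0173 ≈ 57 days. The median is untouched throughout the grid.

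**The case against.** Symmetric windows around a target day are common, and most of what a reader might infer from these does not stand.

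- **Primary and 28-day endpoints.** A reader might infer that up to 3 of 14 or 7 of 60 days are lost for the primary endpoints. The documents do not support this. Later scheduled contacts reach past each of those horizons and collect vital status and readmission. For anyone never reached again, Section 9.3.2 censors at last information and adds worst-case and best-case analyses.
- **Recoveries counted as failures.** Section 9.3.3 censors these participants and codes no failure event. The error is a lost late event and up to 14 days of excess time at risk.
- **First discharge.** It is not exposed to the same degree, for the reason in step 3.
- **Bias between arms.** A reader might suppose that call timing differs by arm in open-label comparisons. The windows are the same for all arms, the one sub-protocol summarised (Section 10.8.1) is double-blind, and nothing in the text suggests arm-dependent timing.
- **Left to the SAP.** Technical detail may be. But Section 9.3.3 already fixes a censoring rule, and a later change of that rule cannot recover recoveries that were never collected.

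What remains of the objection is that the effect is small and confined to secondary endpoints. That limits the severity but does not remove the mismatch.

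**Conclusion.** Wrong as written, and minor. For time to sustained recovery, the protocol allows the last observation 76 days after randomization and then treats the participant as observed without recovery to day 90. This departs from the rule that Section 9.3.2 already uses for the primary endpoints, and no reason is given. The same wording touches first discharge only for participants still in hospital at an early final visit that ends their follow-up.

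The ceiling of 14 of 90 days follows from the text alone. The share of an arm affected, 0.5 to 2.3% with evenly spread calls and 2.0 to 9.0% if every call came on Day 77, rests on the assumed discharge times, recovery shares and call dates. The effect is probably similar in both arms and unlikely to change the median or the conclusion. No sample size is affected.

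**What to change.** 1. In Section 9.3.3, censor participants without the event at the earlier of the last date with known status and day 90, in line with Section 9.3.2. Word this for participants alive at last contact: the status of someone who has died is known through day 90, and the edit should not silently change how deaths are handled.
2. In the synopsis, the schedule of assessments and Section 8, let the Day 91 contact open at the nominal day (for example 0/+14), or keep the window and require a record check at or after Day 91. Record dates of discharge home and of readmission.
3. Leave the Day 15, 29 and 61 windows as they are.

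The first change is one sentence and removes the false time at risk. The second is what recovers the late events. The cost is the loss of the early half of the scheduling window for the final call. Because that window also governs the patient-reported questionnaire (Section 8.2.3) and the stated study duration (synopsis and Section 10.8.1), those passages would need matching edits. The record-check option avoids moving the questionnaire. A later window adds no contact; the record-check option adds one check for participants called early.

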8.1. Core Efficacy Assessments

Planned time points for all efficacy assessments are provided in the SoA (section 1.2). Details of the efficacy assessments are provided below.

8.1.1. WHO COVID-19 disease progression scale

Table 8.1 Modified WHO clinical progression scale

Disease Stage	Descriptor	Score
Uninfected	Uninfected; no viral RNA detected	0
Ambulatory:	Asymptomatic; viral RNA detected	1
mild disease	Symptomatic; independent	2

	Symptomatic; assistance needed	3
Hospitalised: moderate disease	Hospitalised; no oxygen therapy needed*	4
	Hospitalised; need of oxygen by mask or nasal prongs	5
Hospitalised: Severe disease	Need of oxygen by NIV or high flow, re-breather mask or SpO ₂ <90% on room air or 90-94% with a downwards trend and/or signs of respiratory distress**	6
Hospitalised: Critical disease	Intubation and mechanical ventilation, pO ₂ / FiO ₂ ≥150 or SpO ₂ /FiO ₂ ≥200	7
	Mechanical ventilation pO ₂ /FIO ₂ <150 (SpO ₂ /FiO ₂ <200) or vasopressors	8
	Mechanical ventilation pO ₂ /FiO ₂ <150 and vasopressors, dialysis, or ECMO	9
Dead	Dead	10

ECMO = extracorporeal membrane oxygenation, FiO₂ = fraction of inspired oxygen, NIV = non-invasive ventilation, pO₂ = partial pressure of oxygen, SpO₂ = oxygen saturation

*If hospitalised for isolation only, record status as for ambulatory patient.

**persistently increased respiratory rate, use of accessory muscles, inability to complete full sentences. Clinical judgement must be applied to determine whether a low oxygen saturation is indicative of disease progression or severity or is habitual for a given patient (i.e., with underlying chronic lung disease).

A slightly modified version of the original scale¹ will be applied for end point assessment by setting WHO score 6 as a separate stage (severe, not requiring mechanical ventilation) as opposed to WHO score 7-9 (critical, requiring mechanical ventilation), in accordance with WHO treatment guidelines². In addition, the term “need of” is included to account for a situation where the required oxygen therapy is needed but not available. In this case, the WHO score should be based on the level of support needed rather than the level of support received. For assessing indication of oxygen therapy, we refer to recommendations for respiratory support for COVID-19 patients from NIH as well as Surviving sepsis campaign³ for guidance:

- Supplemental oxygen recommended: peripheral SpO₂ < 92% on room air.
- NIV or high flow oxygen recommended: acute hypoxemic respiratory failure despite conventional oxygen therapy.
- Invasive mechanical ventilation recommended: worsening of respiratory status in patients receiving NIV or high flow oxygen OR NIV/high flow oxygen considered insufficient by treating physician.

8.1.2. Oxygen therapy

For all patients included in the study, oxygen saturation (%) shall be measured according to the hospital's regular routines and respiratory rate (RR) shall be counted and registered.

- Patients not receiving oxygen (WHO score 4):
 - Oxygen saturation and RR shall be registered.
- Patients receiving oxygen by nasal prongs and face mask (WHO score 5):
 - Oxygen saturation, RR and numbers of litres of oxygen provided (l/min) and method of oxygen delivery, shall be registered.
- Patients receiving high flow oxygen, NIV or face mask with reservoir (WHO score 6):
 - Oxygen saturation, numbers of litres of oxygen provided (l/min), RR and fraction of inspired oxygen (FiO₂) shall be registered
- Patients that are intubated and on mechanical ventilation (WHO score 7-9):
 - Oxygen saturation and fraction of inspired oxygen shall be registered unless on ECMO.
- Patients on ECMO (WHO score 9):
 - No further information on oxygen therapy will be given.

The SpO₂/FiO₂-ratio will be calculated from registrations of SpO₂ and FiO₂ in patients receiving high flow oxygen, NIV or mechanical ventilation. For other patients, the FiO₂ will be approximated from supplementation of oxygen as described in the table below.

Table 8.2 Estimated FiO₂ % by supplementation of oxygen

Method	O ₂ flow, l/min	Estimated FiO ₂ , %
Nasal Cannula	1	24
	2	28
	3	32
	4	36
	5	40
	6	44

Face mask	1*	24
	2*	28
	3*	32
	4*	36
	5	40
	6	50
	7	55
	>7	55
Face mask with reservoir	4	40
	5	50
	6	60
	7	70
	8	80
	>8	85

8.2. Modular Efficacy Assessments

8.2.1. Viral clearance

Viral load decay will be assessed from oropharyngeal swabs included in the biobank according to a standard operating procedure (level II), as detailed in section 8.4.

